#### 4.4 Study Endpoints

##### 4.4.1 Primary Endpoints

###### 4.4.1.1 Reduction in pain intensity (Brief Pain Inventory)

The primary endpoint of the study is reduction in pain intensity over the past week as measured using the 11-point numerical rating scale of the Brief Pain Inventory (BPI3). The BPI is a widely used and validated assessment designed to measure pain intensity and the interference of pain on daily activities and moods (Cleeland and Ryan, 1994).

The BPI is recommended by the Initiative on Methods, Measurement, and Pain Assessment in Clinical Trials (IMMPACT) panel and has demonstrated validity and reliability across many cultures and languages (Cleeland and Ryan, 1994; Tan et al., 2004; Dworkin et al., 2005). The IMMPACT panel was assembled to develop consensus recommendations to improve and standardize the design and conduct of clinical trials involving treatments for pain. Invited participants included academic centers, regulatory agencies, the National Institutes of Health, the US Veterans Administration, and industry representatives. In addition, the BPI has been used in many chronic pain studies, including those for post-stroke shoulder pain, which demonstrated a significant reduction in pain intensity as compared to a standard of care control (Chae et al., 2005; Yu et al., 2004).

All subjects will be evaluated for a reduction in their worst pain intensity in the previous week (BPI3) at several key study visits: (1) at the completion of the 3-week sham period (Visit 4) to evaluate the placebo effect; (2) at the completion of the 3-week SPR Trial Stage stimulation period (Visit 5) to determine if the subject has met the criteria to be a Trial Stage Success; (3) during the Trial Stage follow-up period to assess for Implant Stage eligibility, and (4) at 3-weeks (Visit 8), 6-weeks (Visit 9), 12-weeks (Visit 10), 6-months (Visit 11), 9-months (Visit 12), 12-months (Visit 13), 24-months (Visit 14), and 36 months (Visit 15) following

the initiation of IPG Stimulation to determine efficacy of the implantable system. The BPI will be administered with stimulation turned off (for at least one hour prior to the study visit) and subjects will be instructed to focus on their shoulder pain when responding to the questions presented in the BPI.

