As a safety precaution to prevent potential excessive bleeding, subjects on warfarin will have blood drawn to confirm an INR of  $<3.0$ . If the INR is not below 3.0, subjects will be given the opportunity to have their warfarin dosage adjusted and the INR will be retested up to two additional times. The INR must be collected within 48 hours prior to the SPR Trial Stage procedure. In addition, a pregnancy test will be conducted in females of reproductive potential.

Once a subject has met all eligibility criteria, the Subject ID will be assigned.

During this visit, subjects will also be assessed for Pain-Free Range of Motion, complete the SF-36v2, complete the BDI-II, and be provided with an Economic

Impact Survey for completion at home. The SULCS and the QST testing (optional) will also be completed at this visit for subjects enrolled following the integration of these tests into the protocol.

Information regarding baseline pain medications (including type, dosage, and frequency) will be collected from the subject and/or their caregiver during this visit. Medications will be categorized as to whether they are used to treat shoulder pain or other types of pain. Subjects will be asked to control these pain medications. They will be instructed that dosages of pain medications should be maintained or can be decreased from their baseline dosage during the week prior to each study visit and phone call for the duration of their study participation. Thus, subjects will be asked to not increase their medication dosages above their baseline dosage during the week prior to each study visit and phone call for the duration of their study participation. The 1-week period was selected because the primary endpoint, BPI pain intensity, asks subjects to recall their worst pain in the past week.

Due to the frequency of visits during the Trial Stage, this medication protocol asks subjects to maintain or decrease their dosages throughout the duration of the Trial Stage. For pain medications that are taken on an as needed basis (e.g. "PRN"), subjects will be queried at baseline for their highest "as needed dose". Future "as needed" dosages during the week prior to the study visits and phone calls should not exceed this dosage.

If pain medication for breakthrough shoulder pain or other types of pain is required beyond their baseline dosage, this will be documented and analyzed in accordance with Sections 6.1 and 6.2.

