This interim analysis will also include an examination of mean changes in the normalized dose of nonopioid medications using pain medication data collected at baseline from the subject (including type, dosage, frequency, and whether the medication is used to treat shoulder pain or other types of pain) compared against each subsequent visit. The analysis will be used to confirm that pain medication dosages did not increase for the week prior to each visit and call and during the Trial Stage follow-up period, in accordance with the study protocol. Although subjects will be asked to maintain pain medication dosages, an increase in dosage for breakthrough pain is permitted. For this pilot study, there is no limit on the number of pain medication uses for breakthrough shoulder pain or other types of pain. The number of uses of breakthrough medication will be analyzed for each subject. Further analysis of this data will be used to evaluate the need for limits on rescue medications for breakthrough pain during the future pivotal study on the implantable system.

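### A mean change in analgesic dose cannot confirm a no-increase rule set for each subject, and breakthrough counts are not tied to the BPI3 recall week

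*Combined protocol and SAP*

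**What the plan says.** **The rule.** Section 4.5.1 states it for the individual: "subjects will be asked to not increase their medication dosages above their baseline dosage during the week prior to each study visit and phone call". With as-needed drugs, the highest as-needed dose reported at baseline is the ceiling, and later "dosages during the week prior to the study visits and phone calls should not exceed this dosage". Subjects may reduce their dose at any time. The window has a stated reason: "The 1-week period was selected because the primary endpoint, BPI pain intensity, asks subjects to recall their worst pain in the past week". Section 4.4.1.1 uses the same week for the primary endpoint: "All subjects will be evaluated for a reduction in their worst pain intensity in the previous week (BPI3) at several key study visits".

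**The exception.** Section 4.5.1 adds: "If pain medication for breakthrough shoulder pain or other types of pain is required beyond their baseline dosage, this will be documented and analyzed", and refers to sections 6.1 and 6.2 for how. Section 6.1.2.4 says: "For this pilot study, there is no limit on the number of pain medication uses for breakthrough shoulder pain or other types of pain". It plans to analyse the number of breakthrough uses for each subject, and to use these data in judging whether the pivotal study needs rescue limits.

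**The check.** Section 6.1.2.4 examines mean changes in normalized non-opioid dose from baseline to each later visit. It gives the purpose as: "The analysis will be used to confirm that pain medication dosages did not increase for the week prior to each visit and call", and extends this to the Trial Stage follow-up period. Section 6.2 repeats the mean at 36 months.

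**Data available.** At baseline, "Medications will be categorized as to whether they are used to treat shoulder pain or other types of pain".

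**The concern.** The statistic and the statement it has to support are at different levels. The rule is broken or kept subject by subject, while the planned summary is one average across subjects. An average can be at or below zero while some subjects are well above their own baseline. A report that followed the plan literally could therefore state that dosages did not increase when some had.

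The second, smaller gap concerns timing. The plan chose the one-week window because BPI3 asks about that week. The count of breakthrough uses has no stated window and no stated link to success status. A reader of the report could not see whether successes at Visit 5 or Visit 10 coincided with extra analgesic in the week being scored.

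**Working it through.** The documents give no doses and no figure to reproduce, so this is a logical check with assumed numbers. The numbers of subjects (up to 45 in the Trial Stage, about 18 in the Implant Stage) come from section 5.4. Normalized dose is not defined in the documents. It is taken here as percent of own baseline, with every subject having a non-zero baseline dose.

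**Step 1: can the mean be zero while some subjects rise?** Let k of n subjects rise by r% and m of the others cut by c%, with the rest unchanged. Then

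mean change = (k × r − m × c) / n.

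- n = 45, k = 4, r = 100, m = 20 (half of the other 41, rounded down), c = 20: (400 − 400) / 45 = 0. Four subjects (8.9%) have doubled their dose.
- n = 18, k = 1, r = 100, m = 8 (half of the other 17, rounded down), c = 20: (100 − 160) / 18 = −3.3%. One subject (5.6%) has doubled.
- n = 45, k = 9, r = 50, m = 18, c = 30: (450 − 540) / 45 = −2.0%. Nine subjects (20%) are above baseline.
- n = 18, k = 4, r = 50, m = 7, c = 30: (200 − 210) / 18 = −0.6%. Four subjects (22%) are above baseline.

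**Step 2: how far does the answer depend on the assumptions?** Completely. If nobody cuts, any rise makes the mean positive, and the largest k is 0. If risers go up by 20% and all others cut by 30%, the condition is 20k ≤ 30(45 − k), so k ≤ 27 of 45. These figures show that cancellation is possible. They neither estimate nor bound how many subjects would rise.

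**Step 3: where is the recall-week link missing?** In the Trial Stage, BPI3 and medication use are queried together every week (Calls 1 and 2, Visit 4, Calls 3 and 4, Visit 5; sections 4.5.2.3 to 4.5.2.8). Uses there can be placed in a recall week, and only the reporting is unspecified. In the Implant Stage, Visit 9 is at week 6 and Visit 10 at week 12. Only the last of those six weeks is scored by BPI3 at Visit 10, so a count without a window mixes it with the other five.

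**Step 4: what is one subject worth?** 1/45 = 2.2 percentage points of the Trial Stage success rate, and 1/18 = 5.6 points of the Implant Stage rate. This is a scale for reading the table proposed below. It does not estimate bias.

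**The case against.** The strongest reply is that the plan already looks at individuals: breakthrough use is documented, counted for each subject and reserved for further analysis. That stands, and it rules out one tempting reading, that increases would go unseen. But a count of uses does not compare dose with baseline, and it is not the analysis that section 6.1.2.4 names for confirming the rule.

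A reader might also infer that medication control ignores the recall week. It does not. The dose rule and the as-needed ceiling are built on that week, and the Trial Stage asks subjects to hold or reduce doses throughout. The missing link concerns only how breakthrough use is reported.

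A reader might fault the logistic regression in section 6.1.2.4 for naming no medication term. The documents do not support that. The list of characteristics is given as examples, and analgesic use at Visit 5 or 10 is post-treatment and may itself respond to pain, so leaving it out is defensible.

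Finally, opioids (apart from the week after implant surgery), injections and slings are barred, so only non-opioid changes are at issue. This is also a pilot that openly leaves breakthrough use unlimited. These facts lower the importance. They do not make the mean fit for its stated purpose.

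**Conclusion.** The mismatch holds: a mean change in dose at or below zero cannot confirm that no subject exceeded his or her own baseline. This follows from the plan's own terms (a per-subject rule, reductions allowed, breakthrough increases permitted) and needs no dose assumption. Only the worked examples do. The breakthrough count also lacks a stated link to the recall week, which matters mainly at Visit 10 in about 18 subjects.

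A reader might go further and infer that extra analgesic inflates the success rate. Nothing in the documents shows that, and the direction is open. Extra doses before Visit 5 or 10 could lower BPI3. Doses taken after a pain peak may leave the worst-pain score unchanged and simply mark a bad week. Extra doses before Visit 4 could lower the reference score and make success harder. The effect may be nil. Importance is low for a pilot.

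**What to change.** Keep the primary endpoint, and keep the mean as a description. In sections 6.1.2.4 and 6.2, base the compliance statement on the number and percentage of subjects above their own baseline dose, or above their as-needed ceiling, in the 7 days before each visit and call where medication use is queried. Cover the Trial Stage follow-up period wherever use is recorded. Section 4.5.2.10 names pain and adverse events for those calls but not medication use, so the report should say how far that period can be checked.

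In the same table:

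- put permitted breakthrough use on a separate line from other increases, so that allowed use is not reported as non-compliance;
- split by shoulder-pain and other-pain medication;
- cross-tabulate with success status at Visits 5 and 10;
- flag subjects with an increase before Visit 4, whose reference score may be lowered.

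An analysis counting subjects with such increases as non-successes is optional and exploratory. It can only equal or fall below the headline rate, it does not correct for extra use before Visit 4, and it penalises use that the protocol permits.

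The cost is wording in section 6 and one table. Medication use is already queried at Calls 1 to 6 and at Visits 4, 5 and 8 to 15, and medication is already categorised by type of pain. This assumes that the case report forms hold dose for the week before each contact, which the planned check already needs. As-needed use that rises but stays within the baseline ceiling is compliant and would not be counted. The table would also serve the plan's own aim of deciding whether the pivotal study needs rescue limits.

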## **6.2 Final Analysis**

A final analysis will be conducted after all subjects have completed the study. This analysis will be on the 36-month IPG Stim ON follow-up visit. The analysis will be identical to the analysis on the 12-week IPG Stim ON data, with the exception that most secondary endpoints are not collected at the 36-month visit. In addition, an examination of mean changes in the normalized dose of nonopioid medications at 36-months will be performed as described in Section 6.1.2.4 above.

## **7.0 STUDY MONITORING AND DEVICE ACCOUNTABILITY PROCEDURES**

### **7.1 Study Monitoring**

#### **7.1.1 Training**

SPR Therapeutics will conduct a Site Initiation and Training Visit prior to initiation of an Investigational Site. The purpose of this visit will be to develop a common understanding of the clinical protocol, CRFs, study specific procedures, Investigator Responsibilities, and Good Clinical Practices (GCPs) among the clinical research monitors and the Investigational Site team.

#### **7.1.2 Routine Monitoring**

Monitoring visits to each Investigational Site will be conducted following the enrollment of the first 2 subjects at the site and then periodically, as determined by the rate of subject enrollment, during the study. These visits are conducted to ensure that the most currently approved version of the Investigational Plan is being followed and that the site is in adherence with all Good Clinical Practices and any specific study Data Monitoring Plan that is in place. In addition, source documents will be reviewed for accuracy against data found on the Case Report Forms.

The Investigational Site will maintain all source documentation in either paper or electronic format. SPR Therapeutics clinical monitors or their authorized representatives will be granted access to these source documents during each visit for verification against the CRFs. The site regulatory files will be reviewed during monitoring visits, as needed, to ensure that current amendments and approvals have been obtained.

The study records may also be subject to a quality assurance audit by SPR Therapeutics (or their authorized representatives), as well as inspection by appropriate regulatory authorities. Site personnel are required to be available

[figure not shown]
during the monitoring visits and audits and ensure that sufficient time is dedicated to this process.

**7.2 Device Accountability**

Device accountability will be maintained by the Investigational Site. The number of devices delivered to the site, clinically used, and returned by the Investigator will be registered. The Investigator is responsible for ensuring that all devices are maintained under controlled conditions with access limited to Investigational study team members. The monitor will reconcile device accountability during the monitoring visits, as needed. Any accountability discrepancies will be explained in writing by the Investigator.

**7.4 Adverse Events and Unanticipated Adverse Device Effects**

Adverse events (AEs) that occur during the study will be captured on CRFs. Specific details regarding any observed AE will be collected on a separate Adverse Event Form. The severity of each Adverse Event will be collected as well as its relationship to the SPR System. AEs will be classified as mild (event that causes mild discomfort or inconvenience and resolves without treatment), moderate (event that requires medical intervention or medication to treat), or severe (event that requires intervention to prevent permanent impairment or damage, an event that requires or prolongs hospitalization, or an event that is disabling, causing permanent damage, life threatening, or causing death). Any necessary treatment or intervention required and the resolution status of the adverse event will also be documented. Adverse Events will be followed to resolution.

An Adverse Device Effect (ADE) is a device-related Adverse Event. All adverse device effects are further categorized as anticipated or unanticipated. Any adverse device effects specified in the Risk Analysis of this Investigational Plan will be considered “anticipated”. All other adverse device effects are considered “unanticipated”. Anticipated events that occur with a greater frequency than expected are also considered unanticipated.

An Unanticipated Adverse Device Effect (UADE) is defined as any serious adverse effect on health or safety or any life threatening problem or death caused by, or associated with, a device, if that effect, problem or death was not previously identified in nature, severity or degree of incidence in this Investigational Plan or application or any other unanticipated serious problem associated with a device that relates to the rights, safety or welfare of subjects.

Study Personnel will report any UADE by telephone and fax within 24 hours of learning of the event. The event is reported by telephone and a completed AE form will be faxed to SPR Therapeutics staff as indicated in **Table 10**. Follow-up information and the complete UADE report will be forwarded to SPR Therapeutics as the event continues and/or resolves.

During Investigator Training, the site will be provided with detailed instructions to report AEs and UADEs. Instructions will be in compliance with SPR Standard Operating Procedures for reporting adverse events in clinical studies. Sponsor contact information for reports of Unanticipated Adverse Device Events is provided in **Table 10**.

**Table 10.** Unanticipated Adverse Device Event Sponsor Contact Information

UNANTICIPATED ADVERSE DEVICE EVENT SPONSOR CONTACT INFORMATION			
Name/Title	Email address	Office Telephone	Fax Number
[REDACTED]	[REDACTED]	[REDACTED]	[REDACTED]
[REDACTED]	[REDACTED]	[REDACTED]	[REDACTED]
[REDACTED]	[REDACTED]	[REDACTED]	[REDACTED]

It is the responsibility of the Investigator to inform his Institutional Review Board (IRB) of any ADEs and UADEs as required by the IRB. In addition, some IRBs will require that AEs that are serious in nature, even if not device related, will be reported as well. SPR Therapeutics is responsible for furnishing the required information to the appropriate regulatory authorities.

## **8.0 RISK BENEFIT ANALYSIS**

The potential risks and benefits to study subjects participating in this study are listed below.

### **8.1 Potential Benefits**

Subjects in this study may not receive any direct benefit by participating in this study. If the treatment is successful, subjects may experience some or all of the following benefits:

- A significant reduction in pain (pain intensity).
- A reduction in degree to which pain interferes with the ability to perform daily tasks (pain interference).

In addition, this research may benefit future patients with post-stroke shoulder pain through knowledge gained or treatments developed through this research.

[figure not shown]
[figure not shown]
## 8.2 Known and Anticipated Risks

### 8.2.1 SPR Trial Stage Risks

The following risks are associated with the SPR System Trial Stage:

#### 1) Risks associated with needle insertion for Smartpatch Lead placement

2) Risk of skin irritation, infection, or inflammation at the Smartpatch Lead exit site

[figure not shown]
3) Risk of the Smartpatch Lead breaking beneath the skin

4) Risk of infection associated with retained Smartpatch Lead fragments

5) Risks associated with lead fragment removal

[figure not shown]
6) Risk of Lead Replacement due to Lead Migration or Lead Becoming Dislodged

A large rectangular area of the page has been completely blacked out, indicating that the information has been redacted.

7) Risk of skin irritation under the Smartpatch Pad, Smartpatch Lead Connector Tape, or bandages

A large rectangular area of the page has been completely blacked out, indicating that the information has been redacted.

[figure not shown]
8) Risk of mechanical or electrical failure of the Smartpatch Stimulator

9) Risks for pregnant women

10) Risk of discomfort due to electrical stimulation

[REDACTED]

[REDACTED]

**11) Risks associated with Diathermy**

[REDACTED]

[REDACTED]

**12) Risks associated with MRI**

[REDACTED]

[REDACTED]

[REDACTED]

[REDACTED]

**13) Risk of allergic reaction to local anesthetics and/or risk of accidental injection of local anesthetic into a vein**

[REDACTED]

[REDACTED]

[REDACTED]

[REDACTED]

**14) Risk associated with venipuncture (if applicable)**

[REDACTED]

[REDACTED]

[REDACTED]

**15) Risk of worsening of pain symptoms**

[REDACTED]

### **8.2.2 SPR Implant Stage Risks**

#### **1) General Risks of Surgery and Anesthesia**

2) Risks of the SPR Implant Stage Procedure

[REDACTED]

**3) Risk associated with venipuncture (if applicable)**

[REDACTED]

[REDACTED]

[REDACTED]

**4) Risk of immunological rejection of the implanted components or materials**

[REDACTED]

**5) Risk of failure of the implanted components of the SPR System**

[REDACTED]

[REDACTED]

[REDACTED]

[REDACTED]

6) Risk of migration of the Implantable Lead or IPG  
[REDACTED]

7) Risk of breakage of the Implantable Lead or a Lead fragment  
remaining in the body if the Lead is removed  
[REDACTED]

[REDACTED]

[REDACTED]

8) Risks of Implantable Lead Fragment Removal

[figure not shown]
9) Risks during pregnancy

10) Risk of mechanical or electrical failure of the IPG Remote.

11) Risk of skin erosion over the Implantable Lead or IPG.

[figure not shown]
12) **Risk of discomfort and/or pain associated with SPR Implant Stage stimulation.**

13) **Risk of skin burns or tissue heating near the IPG.**

14) **Risk of MRI**

15) **Risk of skin irritation associated with the use of the adhesive patches**

16) **Risk of deriving no benefit from the SPR Implant Stage System**

[REDACTED]

17) Risk of worsening of the subject's pain symptoms

[REDACTED]

18) Risk of interference with the SPR System by external radiofrequency sources

[REDACTED]

19) Risk of injury or damage to implantable components

[REDACTED]

